8.2 Assessment and documentation of adverse events

The Research Manager will be notified within 12 hours of any staff member witnessing or becoming aware of a participant reporting an AE. The research staff member will complete an AE data form within 24 hours of knowing about the AE. If a SAE occurs, the Research Manager will notify the lead investigator within 48 hours.

8.3 Eliciting adverse event information

Participants will be asked about the occurrence of any Adverse Events (AE) in the questionnaire completed at the 3 months (completion of program) and 9 months (6 months post completing the program) follow up.

8.4 Adverse event reporting for serious or significant adverse events

Reporting of SAEs will follow The University of Sydney standard operating procedure on clinical trial safety reporting, using the SAE definition and procedures.

9. OUTCOMES

9.1 Primary outcome

The primary outcome physical activity will be assessed using the single item measure of self-reported number of days engaging in at least 30 minutes of moderate physical activity¹².

9.2 Secondary outcome(s)

The self-reported secondary outcomes will be assessed at baseline, 3- and 9-months post baseline using self-report questionnaires and will take approximately 20 minutes to complete. The Short Physical Performance Battery will be assessed at the beginning and end of the 3-month program for the face to face participants. Table 5 presents the outcome measures.

Table 5: Study outcomes and measures

Secondary effectiveness outcomes	Measure
Physical activity- participation in muscle strengthening activity	Single item question: How many days per week do you do muscle strengthening activities, such as resistance training with weights or bodyweight exercises?
Physical activity- participation in functional mobility and balance activity	Single item question: How many days per week do you do activities that emphasise balance and functional mobility training, such as yoga or Tai Chi or home exercises?
Health limitations affecting activities	Short Form 36 health survey
Ability to walk 400m	Self-reported question: Do you have any difficulty walking 400m (that is 2 to 3 blocks) outside on a level ground? (If yes, how much difficulty? Some, Much or Unable to do)
Ability to climb 1 flight of stairs	Self-reported question: Do you have any difficulty walking up 10 steps, that is about one flight, without resting? (If yes, how much difficulty? Some, Much or Unable to do)
Falls and injuries	Number of falls in past 12 months and any fall-related fractures?
Sedentary behaviour	Sedentary behaviour questionnaire
Quality of life	EuroQol EQ-5D-5L
Social Isolation	Social isolation questionnaire
Loneliness Questionnaire	Loneliness lifestyle questionnaire
Balance	Perception of balance: (“Do you feel your balance is excellent, very good, good, fair, poor”)
Fear of falling	(“Are you afraid of falling? (1 = not at all, 2 = little bit, 3 = moderately, 4 = quite a lot, 5 = extremely”)
Adverse Events (measured at follow-up 3 and 9mths only)	Experience any adverse events due to becoming more physically active? Any new or pre-existing condition have resulted in you unable to be physically active?
Short Physical Performance Battery (Face to face participants only)	The Short Physical Performance Battery (SPPB) is an objective assessment tool for evaluating lower extremity functioning.

In addition to the baseline survey participants will complete a demographic and get active form to determine if it is necessary for them to seek further advice from their doctor before becoming more physically active. This information captured will inform us what type of physical activities could be suitable for them during their action plan meeting.

Cost-effectiveness

The intervention and implementation costs will be used to create a decision analytic model to conduct a simulated cost-effectiveness analysis. The cost of delivering the program will be estimated based on trial records where the resources required to implement the program will be recorded (e.g. staff time, any additional non-staff resources) and costed using appropriate wage rates and other relevant cost data.

Utility-based quality of life will be measured using the EQ5D-5L and the health utility score, which is expressed as an index value for health, will be calculated from the 5 questions using published Australian scoring algorithms¹³.

Quality-adjusted life years (QALYs) will be calculated using the health utility score at baseline, and at the 3 and 9-month follow-up. The number of QALYs gained or lost over the 3 and 9 months of follow-up will be calculated by multiplying the time spent in the health state by the relevant health utility score.

Implementation evaluation

Our implementation aims to assess:

- Readiness of delivery partners to implement the *Choose to Move* program.
- Implementation outcomes and determinants that influence implementation of the *Choose to Move* program.

Methods

For this evaluation we will interview and survey delivery partner organisations, activity coaches and participants.

Activity Coaches

We will survey activity coaches to assess five implementation outcomes (effects of deliberate actions to implement; adoption, reach, dose delivered, fidelity and participant responsiveness) and the contextual factors that influence implementation (determinants: feasibility, acceptability, appropriateness) (see Table 6).

To supplement the survey data, we will conduct interviews with all the activity coaches involved in implementing the intervention to collate experiential views about what worked well and areas for improvement (lasting up to 60 minutes). The relationship between insights gained from qualitative analysis and trial outcomes will be explored. Audio recordings (if conducted face to face) or the audio recordings extracted from the video recordings (if completed over Zoom) will be transcribed verbatim by a professional transcription service, REV (rev.com). Video recording will be deleted immediately after the zoom session and only the audio files kept for transcription.

Delivery partner organisation SHARE

To better understand delivery partner organisation SHARE's concepts of implementation strategies designed to build readiness were appropriate and effective, we will conduct a feedback survey and an interview over the phone from the organisation SHARE representative (Director/manager) after final program delivery.

Table 6: Implementation outcomes and determinants

Outcomes	Definition as per McKay et al 2019 ¹⁴	Measurement tool
Reach	Proportion of the intended priority audience (i.e., participants) who participate in the intervention	Screening survey from recruitment website; baseline data form.
Adoption	Proportion and representativeness of providers or the delivery team that deliver an intervention	Study specific document maintained by trial manager
Fidelity	The extent to which an intervention is implemented as it was prescribed in the intervention protocol - by the delivery team	Study specific records to determine extent to which the intervention was delivered as per protocol and extent of delivery if implementation strategies (Table 4)

Dose (delivered)	Intended units of each intervention component delivered to participants by the delivery team	Study specific records to measure the intervention dose delivered and does of implementation strategies delivered (Table 4)
Determinants		
Acceptability (Delivery team)	Perceptions among the delivery team that a given intervention is agreeable, palatable, or satisfactory	Qualitative interviews/ focus groups with delivery team
Acceptability (participants)	Perceptions among the participants that a given intervention is agreeable, palatable, or satisfactory	Includes 1. Study-specific documents on intervention components (e.g., agreement and participation in health coaching sessions); 2. data from number who attended sessions 3. Quantitative survey rating different elements of intervention; 4. Qualitative interviews with sub-group participants.
Cost	Money spent on design, adaptation, and implementation of an intervention	Study-specific log recording costs
Feasibility	Perceptions among the delivery team that an intervention can be successfully used or carried out within a given organisation or setting	Qualitative interviews with delivery team
Context	Aspects of the larger social, political, and economic environment that may influence intervention implementation	Field notes kept by Research Manager based on Consolidated Framework for Implementation Research (CFIR)
Adaptability	Extent to which an intervention can be adapted, tailored, refined, or reinvented to meet local needs	Study-specific document guided by expanded Framework for Reporting Adaptations and Modifications to Evidence-based interventions (FRAME) framework (Wiltsey Stirman et al Imp Sci 2019)
Potential for Scale-up	The scalability (the ability of a health intervention shown to be efficacious on a small scale and/or under controlled conditions to be expanded under real world conditions to reach a greater proportion of the eligible population while retaining effectiveness of a discrete health program or intervention	Intervention Scalability Assessment Tool (ISAT) ¹⁵

Participants

In terms of acceptability, barriers and facilitators, participants' experiences of the program will be explored via post-intervention 'Impressions' surveys (sent to all participants after the 3-month program) and via semi-structured interviews with up to 30 purposively sampled participants, selected for maximum variation in age, geographical location, socio-economic status, carer responsibilities and engagement with the intervention (as reported in their Impressions survey). Questions in the survey and interviews will cover attractions and expectations of the program, views of the program and its components, any impacts, accounts of continuing/discontinuing participation, and questions related to the underlying program theory phrased in lay language. Qualitative data from free text comments in the surveys, and from transcriptions of the semi-structured interviews, will be analysed thematically.

It is estimated 20-30 participants will be invited to participate in a 30–40-minute telephone interview by a member of the research team who has experience in qualitative methods, after the completion of the 3-month study period. Participants will be informed at the beginning of the interview that it will be audio recorded. All interviews will be audio recorded and transcribed verbatim by a professional transcription service, REV (rev.com) and securely stored on the University of Sydney password protected research data store (RDS). Once the interviews are transcribed the audio files will be destroyed securely as per the University of Sydney guidelines. Participants will have the opportunity to review their individual responses after the transcription has been completed if they wish. If the program is effective, this process evaluation information will be used to guide future design for implementation at scale, including approaches for different participant profiles and contexts.

Delivery partner organisation representatives/Activity coaches

Questions in the follow up survey and interviews will be completed by all activity coaches and the representative SHARE organisation directors/managers. The topics will cover facilitators and expectations of the program, views of the program components, the impact of the program, accounts of continuing/discontinuing participation in program and questions related to the underlying program theory. All surveys and interviews will be phrased in lay language. Qualitative data from free text comments in the surveys and from transcriptions of the semi-structured interviews will be analysed thematically.

It is estimated up to 5 activity coaches and 2 organisation directors/ managers will be invited to participate in a 30–40-minute telephone interview by a member of the research team who has experience in qualitative methods, after the completion of the study period. They will be informed at the beginning of the interview that it will be audio recorded. All interviews will be audio recorded and transcribed verbatim by a professional transcription service, REV (rev.com) and securely stored on the University of Sydney password protected research data store (RDS). Once the interviews are transcribed, the audio files will be destroyed securely as per the University of Sydney guidelines. Activity coaches/delivery partner organisation representatives will have the opportunity to review their individual responses after the transcription has been completed if they wish. If the program is effective, this process evaluation information will be used to guide future design for implementation at scale, including approaches for different participant profiles and contexts.

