
OUTCOMES
	
Primary effectiveness outcome: Physical activity (PA) will be assessed using the single item measure of self-reported number of days engaging in at least 30 minutes of moderate physical activity per week.
 
Secondary effectiveness outcomes: Self-reported single item questions about days per week doing muscle strengthening activities and balance training, ability to walk 400m and 1 flight of stairs, health limitations affecting activities, sedentary behaviour, quality of life, social isolation, loneliness, perception of balance, fear of falling, number of falls in past 12 months, adverse events at follow up and Short Physical Performance Battery.
 
Implementation outcomes: Reach, adoption, fidelity, dose, sustainability.
 
Implementation determinants: Acceptability, cost, feasibility, adaptability, compatibility, culture, complexity, self-efficacy
 
Qualitative outcomes: Participant acceptability, barriers, facilitators, and participant experience.
 
Cost outcomes: Study-specific logs will be used to record costs associated with design, adaptation and intervention delivery and could be used to create a decision analytic model to conduct a simulated cost-effectiveness analysis.

STUDY DURATION
	
We aim to recruit all participants between Oct 2024 and December 2026. Data analysis and report writing will be completed by December 2027.

INTERVENTION/S
	
Choose to Move is a 3-month program that provides motivation and support for adults aged 50 years and over to become more physically active and socially connected. Participants work with a trained activity coach in groups to set health goals and develop a personalised physical activity plan.
 
The program involves:
 
 • One-one consultation action planning (30min). • Group meetings (8x1 hour sessions over 3 months): Activity coaches will deliver education on various health topics, share community resources and facilitate group discussions. • Access to the Choose to Move website. • Access to the Choose to Move Facebook group. • Resources - group meeting PowerPoint presentations, handouts and fortnightly newsletters).

NUMBER OF PARTICIPANTS
	
16 programs with average of 10 participants per program will provide a total of 160 participants.

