6. RESEARCH PLAN / STUDY DESIGN

6.1 Type of study

This is an uncontrolled, single group implementation study that is focused on implementing the *Choose to Move* program across Sydney, Australia. This will be through a process of:

1. Adaptation: Co-design implementation strategies to adapt the program for adults in Sydney.
2. Intervention: Deliver 3-month intervention, build organisation capacity and support delivery partners on implementation
3. Evaluation: Measure the acceptability and adherence of the CTM program
4. Evaluation: Describe and assess implementation strategies used to achieve 'best fit' and to measure CTM program benefits for various health outcomes.

6.2 Population / Sample size including power calculation.

16 programs with an average of 10 participants per program will provide a total of 160 participants to detect a difference in the proportion of participants who increase their physical activity level from baseline to 3-months (approximately 1 day/week), allowing for 20% dropout.

Sample Size: To attain >80% power to detect an increase in PA of approximately 1 day/wk as per CTM Phase 3 (PA by the single-item measure; T1 = 2.5 d/wk.; T2 = 3.4 d/wk.; SD difference = 2.2) with alpha of 0.05 across two comparisons (T2 vs.T1), an intraclass correlation for PA of 0.05 (to account for the clustered design of participants within programs) and estimated 20% drop out.

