6.5.3 Randomisation and blinding processes

This is a non-randomised study. All participants will receive the *Choose to Move* program for 3 months, so masking is not required. Figure 1 shows the flow of participants through the *Choose to Move* program.

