6.5.4 Schedule of events

The timing of the *Choose to Move* intervention components over the 12-week period is outlined in Table 2. The timing for measures collected for relevant stakeholders are outlined in Table 3.

Table 2: *Choose to Move* component delivery timeline.

Program Week		1	2	3	4	5	6	7	8	9	10	11	12
Information Session	●												
Motivational Group Meeting		●		●	●	●	●		●		●		●
One-on-One Consultation			●										

[figure not shown]
Note: the weeks may be slightly adjusted based on room availability at the delivery organisations venue and other unforeseen events such as public holidays.

Table 3: Overview of measures collected for each participant group and various time points.

Participant group	Measures	Planning (T0)	Baseline of Program (T1)	3 months (on completion of program) (T2)	9 months (6 months post program) (T3)
Participants	Demographic and Get Active Forms		Y		
	Outcome measures survey		Y	Y	Y
	Impressions of the choose to move program survey (end of program feedback)			Y	
	Interviews (subset) end of program			Y	
Activity Coach	Training Survey	Y			
	Feedback Survey			Y	
	Interview (subset) end of program			Y	
Organisations representatives (Director/manager) (SHARE)	Feedback Survey end of program			Y*	
	Interview (Directors/manager) end of program			Y*	

*Follow up survey and interview by organisation representative will only be completed at the end of the last program delivery.

Figure 1. Flow of participants

Choose to Move and implementation strategies for Sydney

The research project team will engage with participants and partner organisation SHARE in an adaption process to adapt the *Choose to Move* program to achieve the best fit and identify specific implementation strategies (e.g. training, recruitment) that align with the priorities and capacity of the delivery partner SHARE that will implement the program.

What support do organisations receive?

The team at the University of Sydney will work with partner organisation SHARE to understand how *Choose to Move* might fit and complement their existing programs and activities (Table 4). SHARE will receive funding to cover delivery costs for staff.

Table 4: The support provided to organisations (implementation strategies).

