6.11 Continuation of therapy

Following the 3-month program, participants will continue to have access to the *Choose to Move* Facebook page, newsletters, and the website as they are public and readily available. If they have joined external classes, they can continue participating, however access to an activity coach will cease after the program finishes.

Participants will be followed up 6 months after the completion of the program to see if any activity they have commenced has been maintained (see Table 3). In addition, we will record any adverse events such as falls, musculoskeletal injury or cardiovascular events that has occurred post program that has reduced the ability to maintain being physically active.

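### The falls item looks back 12 months at every survey, so only about a quarter of any relative change in falls shows at 3 months and three quarters at 9 months

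*Protocol*

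**What the plan says.** Falls are a secondary effectiveness outcome. The synopsis lists "number of falls in past 12 months", and Table 5 in section 9.2 gives the measure as "Number of falls in past 12 months and any fall-related fractures". Twelve months is the only look-back stated.

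On timing, section 9.2 says: "The self-reported secondary outcomes will be assessed at baseline, 3- and 9-months post baseline using self-report questionnaires". Table 3 in section 6.5.4 schedules the outcome survey at baseline (T1), at 3 months (T2) and at "9 months (6 months post program) (T3"). Where timing differs, the protocol says so: Table 5 has "Adverse Events (measured at follow-up 3 and 9mths only"), and the text above the table limits the physical performance battery to the start and end of the program. The falls row carries no such exception.

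Section 6.1 describes the design: "This is an uncontrolled, single group implementation study". Any effect on falls must therefore be read from the same people before and after the program starts.

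**The concern.** A before-after comparison needs a follow-up window that begins when the program begins. Here the look-back is longer than the time since baseline at both follow-ups, so each follow-up answer mixes falls from before and after program start and repeats part of the baseline answer. A single 12-month total cannot be split afterwards, so no analysis plan can recover the missing detail. The choice is fixed when the question is asked.

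At stake is the falls and fall-related fracture result, in either direction. A reduction would look smaller than it is. So would an increase, which matters in a program that encourages inactive people aged 50 and over to become more active.

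**Working it through.** **Inputs**
- Look-back: 12 months (synopsis; Table 5).
- Surveys at t = 0, 3 and 9 months (section 9.2; Table 3).
- Program: months 0 to 3 (section 6.5.3). Baseline is taken as program start.
- Completers: 160 × (1 − 0.20) = 128 (section 6.2).
- Fall rate and program effect on falls: not given. Assumed 0.3 to 1.0 falls per person-year and rate ratios (RR) of 0.5 to 0.9.

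The protocol states no figure for falls, so there is none to reproduce.

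**Step 1: windows.** A survey at month t covers months t − 12 to t. The pre-program share, which is also the overlap with the baseline window, is (12 − t)/12.

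| Survey | Window (months) | Pre-program share |
|---|---|---|
| T1 | −12 to 0 | 12/12 = 100% |
| T2 | −9 to +3 | 9/12 = 75% |
| T3 | −3 to +9 | 3/12 = 25% |

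Months 0 to 3 fall inside both the T2 and the T3 windows.

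**Step 2: ratio that would be observed.** With a constant underlying rate, the expected ratio to baseline is [(12 − t) + t × RR]/12.

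| True RR | Seen at 3 months | Seen at 9 months |
|---|---|---|
| 0.9 | 0.975 | 0.925 |
| 0.8 | 0.950 | 0.850 |
| 0.7 | 0.925 | 0.775 |
| 0.5 | (9 + 1.5)/12 = 0.875 | (3 + 4.5)/12 = 0.625 |

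The visible share of a relative change is t/12: 25% at 3 months and 75% at 9 months. The same applies to harm. A true ratio of 1.5 would appear as (9 + 4.5)/12 = 1.125 and (3 + 13.5)/12 = 1.375.

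**Step 3: within-person difference.** If the shared months are reported identically on both occasions, they cancel:
- T2 − T1 = falls in months 0 to 3 minus falls in months −12 to −9.
- T3 − T1 = falls in months 0 to 9 minus falls in months −12 to −3.

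The absolute change is then not diluted. But this needs identical recall of the shared months, and at 3 months the comparison quarter is the most remote one recalled at baseline.

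**Step 4: what rewording can and cannot gain at 3 months.** Take Poisson counts, consistent recall, no clustering and a two-sided 0.05 test. The expected difference is d = rate × (t/12) × (1 − RR), its variance per person is v = rate × (t/12) × (1 + RR), and power is Φ(d√128/√v − 1.96). For example, at t = 3, rate 0.3 and RR 0.7: d = 0.0225, v = 0.1275, and power is 11%.

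| True RR | Power at 3 months, rate 0.3 to 1.0 | Power at 9 months, rate 0.3 to 1.0 |
|---|---|---|
| 0.7 | 11% to 26% | 23% to 62% |
| 0.5 | 24% to 64% | 59% to 98% |

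Comparing a past-3-month item at baseline with a past-3-month item at T2 has the same d and v, hence the same power. What it removes is the diluted ratio and the dependence on identical repeated recall.

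**The case against.** A reader might infer that the before-after comparison cannot show any effect on falls. The documents do not support that. Three quarters of the 9-month window follows program start, and three quarters of a relative effect stays visible there. With consistent recall, the shared months cancel in the within-person difference, and the 3-month contrast is then even matched for season. Both points stand. They limit the defect but do not remove it, because identical recall on repeated occasions is a strong requirement.

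A reader might also infer that a rise in falls would go unseen. That too goes beyond the text. Section 8.1 names falls as adverse events, section 8.2 sets notification times, section 8.3 asks about events at 3 and 9 months, sections 6.9 and 6.12 provide for an independent monitoring board, and under section 6.11 "we will record any adverse events such as falls, musculoskeletal injury or cardiovascular events that has occurred post program". The cover is partial: section 8.1 counts events during physical activity, the adverse-event row of Table 5 asks about events due to greater activity, and section 6.11 concerns those that reduced the ability to stay active. The falls item remains the only all-cause fall count with a baseline comparator.

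Two further objections stand. Low information at 3 months comes largely from the short exposure of a modest sample, which rewording does not cure (step 4). And the baseline, 3-month and post-program survey forms are listed as separate appendices (section 15) but not shown, so the follow-up forms may already use another window. In that case the synopsis and Table 5 describe the outcome wrongly, and a correction is still needed.

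**Conclusion.** The point holds as a dilution and overlap problem. On the protocol's wording, the 3-month falls answer is 75% pre-program time and the 9-month answer 25%, both already covered at baseline. About a quarter of a relative change shows at 3 months and three quarters at 9 months. The shares follow from the stated window and schedule alone. The ratios also assume a constant underlying rate and an effect that starts at baseline, and the power figures rest on assumed fall rates and effects.

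This should be fixed, but it is not critical. Falls are one of many secondary outcomes, and the primary outcome and the sample size are unaffected. It would be wrong to conclude that a better window makes the falls result causal: the study has no control group, and that limit remains whatever the recall period.

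**What to change.** In Table 5 and the synopsis, state the look-back for each survey:
- **Baseline:** keep the 12-month item. Optionally add a past-3-month item for a like-for-like comparison at 3 months.
- **3 months:** falls and fall-related fractures since program start.
- **9 months:** falls and fall-related fractures since the 3-month survey, or since program start for anyone who missed that survey.

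Report falls as a rate per person-month, with the combined 0 to 9 month rate as the main follow-up figure. The model can be left to the analysis plan. The pre-program share then falls to 0% at both follow-ups, and under the same assumptions the expected ratio equals the true one: 0.70 appears as 0.70, not as 0.925 or 0.775. If the survey forms already use shorter windows, correct the synopsis and Table 5 instead.

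The cost is a reworded follow-up item, an optional extra baseline item, and a survey amendment needing ethics approval before use (section 6.8). Recruitment is planned to December 2026, so an early change protects more data; follow-up answers already given over 12 months cannot be converted and should be kept apart. The downsides are fewer falls in each shorter window, no power gain for the like-for-like 3-month comparison, possible seasonal differences between windows, and different recall lengths when a 12-month baseline is set against shorter follow-up periods.

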8. SAFETY CONSIDERATIONS

8.1 Adverse event definitions

Adverse events (AEs) are defined as “incidents in which harm resulted to a person receiving health care”. For this research study, an AE is defined as an unwanted and usually harmful outcome (e.g. fall, seizure, cardiac event). The event may or may not be related to the intervention, but it occurs while the person is participating in the intervention, i.e. while they are doing physical activity. Adverse events will be categorised as minor AEs (MAEs) or serious AEs (SAEs). A MAE is defined as an incident that occurs while the person is participating in the intervention that results in no injury or minor injury. For example, a fall where the person sustains a small cut or bruise that requires none or minor medical intervention. A SAE is defined as an incident that occurs while the person is participating in the intervention that results in death, serious injury or re-hospitalisation. Examples of SAEs are:

- Death
- Myocardial infarction
- Serious falls
- Serious fractures

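### The second adverse-event question in Table 5 does not match the definition in section 8.1 or the scope in 6.11, and a yes cannot be sorted into new, worsened or unchanged

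*Protocol*

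**What the plan says.** Table 5 in section 9.2 has one adverse-event row, labelled "Adverse Events (measured at follow-up 3 and 9mths only", with two questions. The first carries an attribution: "Experience any adverse events due to becoming more physically active". The second does not: "Any new or pre-existing condition have resulted in you unable to be physically active". The synopsis lists adverse events at follow-up among the secondary effectiveness outcomes.

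Section 8.3 makes the surveys the planned way of eliciting events: "Participants will be asked about the occurrence of any Adverse Events (AE) in the questionnaire completed at the 3 months", and again at 9 months.

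Section 8.1 defines what counts. On relatedness and timing it says "The event may or may not be related to the intervention, but it occurs while the person is participating in the intervention", and it explains the timing as "i.e. while they are doing physical activity".

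Section 6.11 gives another scope. At the follow-up six months after the program, the team will record falls, injuries or cardiovascular events that arose after the program and reduced the person's ability to stay active.

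Three other provisions bear on the point. Section 6.1 describes a single-group study without a control. Section 6.5.1 excludes people whose medical condition rules out regular activity. Sections 6.9 and 6.12 have an independent board monitor adverse events.

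**The concern.** The definition in 8.1 asks when and in what setting an event occurred. The second survey question asks neither. It asks whether some condition, new or old, left the person unable to be active. That is a question about reasons for inactivity, placed under an adverse-event label.

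Two things are at stake. First, the safety result becomes hard to read. The study has no comparison group to show how often adults of this age report such conditions anyway, so the question itself has to carry the information on onset. Second, the protocol leaves open whether a yes to this question is an adverse event for reporting under 8.2 and for the monitoring board. With no recall period, one long-standing condition can also be reported at 3 months and again at 9 months.

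**Working it through.** The protocol states no adverse-event rate, count or threshold, so there is no figure to reproduce. The check sets the scopes side by side.

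| Source | Onset required | Setting or attribution required | Consequence required |
|---|---|---|---|
| Section 8.1 | During participation | While being active; relatedness not required | Unwanted, usually harmful outcome |
| Section 6.11 | After the program | None stated | Reduced ability to stay active |
| Table 5, first question | None stated | Due to becoming more active | None |
| Table 5, second question | None; old conditions expressly included | None | Unable to be active |

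Four cases, read literally, show where these part:

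1. *New injury during a planned walk in the program, leaving the person unable to be active.* It meets 8.1 and gives a yes to both questions.
2. *New illness arising away from any activity, leaving the person unable to be active.* It is outside the activity wording of 8.1, but gives a yes to the second question.
3. *Old joint problem that flares after the program.* It plausibly fits 6.11. It fits 8.1 only if it arose during activity. It gives a yes to the second question if the person became unable to be active.
4. *Old condition, unchanged, that the person gives as the reason for not being active.* It is outside 8.1 and 6.11, but gives a yes to the second question.

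Cases 1 to 4 all give the same answer to the second question.

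**What that answer can identify.** Let p be the proportion answering yes, made up of new (n), worsened (w) and unchanged (u) conditions, so p = n + w + u. Only p is observed. From this question alone, n + w can lie anywhere from 0 to p. With 160 enrolled and the planned 20% dropout, 160 × 0.80 = 128 people are followed. If p were 2% to 20% (an assumption), the yes answers would come from 128 × 0.02 = 2.6 to 128 × 0.20 = 25.6 people. The number with a new or worsened condition could be anything from none to all of them.

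**If the two questions were pooled.** This is an illustration only. It assumes an either-question rule, independence, attributed events (h) in 2% to 10%, and a yes to the second question (b) in 2% to 20%. The pooled proportion is 1 − (1 − h)(1 − b).

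- Lowest: 1 − 0.98 × 0.98 = 4.0%, or 128 × 0.0396 = 5.1 people.
- Middle: h = 5%, b = 10% gives 1 − 0.95 × 0.90 = 14.5%, or 18.6 people against 128 × 0.05 = 6.4 with an attributed event.
- Highest: 1 − 0.90 × 0.80 = 28.0%, or 35.8 people.

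Neither the rates nor the pooling rule comes from the protocol, so these figures show only that the answer depends on choices the text leaves open.

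**The case against.** A reader might infer that the adverse-event result will be inflated by background illness passed off as program harm, and that the lack of a baseline answer makes this uncorrectable. The documents do not support that reading, for these reasons:

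- No section combines the two questions into one proportion. The first question already isolates events attributed to increased activity and can be reported alone. How the two are tabulated may be settled in a statistical analysis plan that is not shown.
- Section 8.1 accepts unrelated events, so collecting them is not in itself an error.
- People whose condition rules out regular activity are excluded. A later yes to a question about being unable to be active should therefore mostly reflect something new, worsened or recurrent. Worsening can be a genuine adverse event, and adverse events do not normally need a baseline value to subtract.
- Other data exist. The Get Active form is completed at baseline; health limitations, walking 400 m and stair climbing are asked at all three times; and section 8.2 has staff complete an event form once they learn of an event.
- Table 5 may only summarise the questions. The surveys are listed as appendices and are not shown; they may hold onset or free-text fields.

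All of this limits the size of the problem, and the baseline point falls away. What remains is the mismatch. Separate reporting protects the first question but does not help within the second, where the three kinds of yes stay merged. The exclusion does not cover intermittent or partial conditions, and the printed wording expressly invites old ones. No section links the baseline form or the function items to the adverse-event answers, or says that a yes to the second question triggers an event form.

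**Conclusion.** The point holds as a mismatch between definition and measurement. The second question, as printed in Table 5, collects conditions that fall outside both 8.1 and 6.11, and its answers cannot be divided afterwards into new, worsened and unchanged. Sections 8.1, 6.11 and Table 5 also differ among themselves on what an adverse event is.

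The size of the distortion cannot be derived. Any multiple of the true rate would rest on assumed rates and an assumed pooling rule, and the eligibility criteria give reason to expect that the unchanged group is limited. The conclusion rests on Table 5 giving the substance of the questions as asked. If the actual surveys already record onset or worsening, only the reconciliation of the three places remains. Either way this is an inexpensive improvement to how readable the safety result is. It is not a defect that undermines the study.

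**What to change.** 1. Reconcile section 8.1, section 6.11 and Table 5 so that they state one scope for an adverse event, including whether the activity condition in 8.1 applies and how events after the program are treated. Rewording the question alone would not do this: a new or worsened condition arising away from activity would still be outside 8.1 as written.
2. In the 3- and 9-month surveys, split the second question into three answers: a new condition, an existing condition that became worse, and an existing condition that is unchanged. Refer each to the time since program start (3 months) or since the last survey (9 months).
3. Report this question separately from the one on events due to becoming more active. Do not count unchanged conditions as adverse events; report them as reasons for not being active.

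No extra baseline question is needed. The cost is a minor survey amendment submitted to the ethics committee and slightly longer surveys. Answers collected before the change cannot be split and should be shown apart.
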